### **3.1.1 Treatment Flow**

The study will consist of 4 phases: Screening, Treatment, Follow-up and Survival Follow-up.

#### **Screening Phase:**

- Begins by establishing the subject's initial eligibility and signing of the informed consent form (ICF)
- Subject is enrolled using the Interactive Voice Response System (IVRS).
- Tumor tissue from an unresectable or metastatic site of disease must be provided for biomarker analysis. Central lab must provide IVRS with confirmation of receipt of evaluable tumor tissue prior to subject randomization (for subjects in the 1L Nivolumab vs Sorafenib Cohort and Nivolumab plus Ipilimumab Combination Cohort).
- Screening assessments can be performed within 28 days of first dose.

#### **Treatment Phase:**

Nivolumab monotherapy will be given on an every two week schedule and one treatment cycle (42 days) is comprised of three doses in the Dose Escalation (at doses of 0.1 mg/kg to 10 mg/kg q2week) and Expansion Phase (3 mg/kg q2week). In the 1L Nivolumab vs Sorafenib Cohort, nivolumab monotherapy (240 mg IV) will be given on an every two week schedule with 1 dose = 1 cycle; sorafenib will be given 400 mg po BID. In the Nivolumab plus Ipilimumab Combination Cohort, the dosing will be as outlined above, with no less than 19 days between doses in Arms A and B during the q3week induction phase. In arm C, nivolumab doses may be given no less than 12 days between doses, and ipilimumab doses no less than 5 weeks between scheduled doses

All subjects except those in the 1L Nivolumab vs Sorafenib Cohort will undergo tumor assessments at every q6 week ( $\pm$  2 days) for the first 48 weeks, and then q12 week ( $\pm$  1 week) thereafter until disease progression. Subjects in 1L Nivolumab vs Sorafenib Cohort will undergo tumor assessments q8 week ( $\pm$  1 week) for the first 48 weeks, and then q12week ( $\pm$  1 week) thereafter until disease progression or treatment is discontinued (whichever occurs later). Imaging assessments should be scheduled regardless of dose delay or missed doses in all cohorts.

Prior to activation of Amendment 8, subjects in the Dose Escalation Phase were treated until either a confirmed CR, completion of 2 years of therapy, toxicity, or disease progression. However, upon activation of Amendment 8, all subjects are to be treated until toxicity, RECIST 1.1 defined progression ([Appendix 2](#)), unacceptable toxicity, or study discontinuation for any other reason ([Section 3.5](#)). Treatment may continue beyond progression under protocol defined.

Subjects will continue to receive nivolumab, sorafenib, or nivolumab plus ipilimumab until:

1. RECIST 1.1-defined radiographic progression or unacceptable toxicity.
2. Clinical deterioration ([Section 3.1.4](#)) suggesting that no further benefit from treatment is likely.
3. Meets criteria for discontinuation of study therapy as outlined in [Sections 3.1.3.1](#) (Dose Limiting Toxicity), [3.5](#) (Discontinuation of Subjects from Treatment), [4.1.18](#) (Nivolumab Permanent Discontinuation Criteria), [4.1.12](#) (Treatment Interruption or Discontinuation for Sorafenib Treatment) or [4.2](#) (Ipilimumab Permanent Discontinuation Criteria)

Accumulating evidence indicates that the emergence of objective responses to agents that activate anti-tumor immune responses follows delayed kinetics of weeks or months, and can be preceded by initial apparent radiological progression or the appearance of new lesions or some enlarging lesions while certain target lesions are regressing (“mixed response”). It is thus reasonable, in the absence of clinical deterioration, to continue to treat these subjects until progression is both confirmed and found to have worsened at a subsequent imaging evaluation. Evidence of PD will be based on a comparison with baseline (or nadir) scans or other tumor evaluations. Additional details on treatment beyond progression are located in [Sections 3.1.8](#) (for nivolumab and ipilimumab) and [4.1.13](#) (for sorafenib).

No subject receiving nivolumab or nivolumab plus ipilimumab will be permitted dose escalations or de-escalations. Sorafenib dose adjustments are described in [Section 4.1.8](#) circumstances ([Section 3.1.8](#)). After discontinuation from study therapy, there are 2 follow-up visits required (on site visits), and additional survival follow-up (on-site or phone visits).

#### **Follow Up Phase:**

Follow-Up Visit 1 to occur 35 days from the last dose ( $\pm$  7 days) or coinciding with the date of discontinuation of study drug ( $\pm$  7 days) if the date of discontinuation is greater than 42 days from the last dose. Follow-Up Visit 2 to occur 80 days from Follow-Up Visit 1 ( $\pm$  7 days).

Subjects who discontinue study drug for reasons other than radiographic progression or who continue treatment beyond progression will continue to have tumor assessments (if clinically feasible) according to the schedule in [Table 5.1-8](#) and [Table 5.1-9](#) and until progression or treatment discontinuation for subjects being treated beyond progression.

Subjects will be followed for drug-related toxicities until these toxicities resolve, return to baseline or are deemed irreversible. All adverse events will be documented for a minimum of 100 days after the last dose of study drug.

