### **1.3 Objectives(s)**

#### **1.3.1 Primary Objectives**

- **Dose Escalation Phase**: To establish the safety, tolerability, dose limiting toxicities (DLT) and maximum tolerated dose (MTD) for nivolumab administered every 14 days to subjects with advanced HCC.
- **Expansion Phase**: To estimate the ORR and duration of response of nivolumab monotherapy in subjects with advanced HCC who are naive to sorafenib or have been previously treated with sorafenib. ORR will be determined with a blinded independent central review (BICR) assessed tumor response based on RECIST 1.1.
- **1L Nivolumab vs Sorafenib Cohort**: To estimate overall response rate (ORR) of nivolumab and sorafenib in subjects with advanced HCC who are naive to systemic therapy. ORR will be determined with Investigator assessed tumor response based on RECIST 1.1.
- **Nivolumab plus Ipilimumab Combination Cohort**:
  - To establish the safety and tolerability of nivolumab plus ipilimumab in subjects with advanced HCC.
  - To estimate the ORR and duration of response for nivolumab plus ipilimumab combination therapy in subjects with advanced HCC who have been previously treated with sorafenib. ORR will be determined with Investigator assessed tumor response based on RECIST 1.1.

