#### **1.3.2 Secondary Objectives**

- **Escalation and Expansion Phase**:
  - To assess antitumor activities (Time to Progression (TTP) and Progression Free Survival (PFS)) based on results of blinded independent central review (BICR) and/or investigators using RECIST 1.1.
  - To evaluate overall survival (OS) in subjects treated with nivolumab monotherapy.
  - To investigate the potential association between selected biomarker measures, such as PD-L1 expression, and clinical efficacy measures including overall survival.

- To characterize the pharmacokinetics of nivolumab in subjects with advanced HCC (Dose Escalation Phase only).
- To assess the immunogenicity of nivolumab in subjects with advanced HCC (Dose Escalation Phase only).
- **1L Nivolumab vs Sorafenib Cohort:**
  - To estimate TTP and PFS of nivolumab and sorafenib in subjects with advanced HCC who are naive to systemic therapy.
  - To evaluate the overall survival (OS) of nivolumab and sorafenib in subjects with advanced HCC who are naive to systemic therapy.
  - To evaluate the relationship between PD-L1 expression and efficacy.
- **Nivolumab plus Ipilimumab Combination Cohort:**
  - To assess antitumor activities (TTP and PFS) based on results of BICR and/or investigators using RECIST 1.1.
  - To evaluate overall survival (OS) in subjects treated with nivolumab plus ipilimumab.
  - To investigate the potential association between selected biomarker measures, such as PD-L1 expression, and clinical efficacy measures including overall survival.

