### **3.4.3 Palliative Local Therapy**

Palliative local therapy for clinically symptomatic tumor sites (eg bone pain) including palliative (limited-field) radiation and palliative surgical resection may be considered if the following criteria are met:

- The subject is considered to have progressed at the time of palliative therapy and meets criteria to continue with treatment beyond progression ([Section 3.1.8](#)).
- The lesion for palliative local therapy is a non-target lesion
- The case is discussed with the BMS medical monitor. Palliative therapy must be clearly documented as such in the study record.
- Tumor lesions requiring palliative local therapy should be evaluated for objective evidence of disease progression prior to the initiation of such therapy. In addition, sites must request an Independent Review of Progression from the third party radiology vendor prior to the initiation of palliative local therapy. However, the initiation of palliative local therapy need not be delayed to await the assessment by the Independent Review of Progression.
- Palliative therapy must be clearly documented in the source records and electronic case report form. Details in the source records should include: dates of treatment, anatomical site, dose administered and fractionation schedule, and adverse events.

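### BICR-read duration of response, TTP and PFS are open to informative censoring, probably upward, because subjects who stop drug for site-read radiographic progression leave the scan schedule

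*Combined protocol and SAP*

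**What the plan says.** **Scan schedule.** Section 3.1.1 (Treatment Phase) states: "All subjects except those in the 1L Nivolumab vs Sorafenib Cohort will undergo tumor assessments at every q6 week", "for the first 48 weeks, and then q12 week", up to disease progression. In the 1L cohort scans are every 8 weeks to Week 48 and then every 12 weeks, ending at the later of progression and end of treatment.

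**After drug is stopped.** The Follow Up Phase text says: "Subjects who discontinue study drug for reasons other than radiographic progression or who continue treatment beyond progression will continue to have tumor assessments". Those scans run "and until progression or treatment discontinuation for subjects being treated beyond progression". A subject who stops for radiographic progression is in neither group.

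**Whose progression.** Neither passage names the reader. Sections 3.1.8 and 4.1.13 tie the decision to treat past progression to the investigator's assessment. They also fix the progression date of subjects treated beyond progression, but only for investigator-read analyses. The one request for central reading of progression in the text reviewed is in Section 3.4.3: "sites must request an Independent Review of Progression from the third party radiology vendor prior to the initiation of palliative local therapy". The palliative therapy need not wait for the result.

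**Which reader for the endpoints.** For the combination cohort, Section 1.3.2 has: "To assess antitumor activities (TTP and PFS) based on results of BICR and/or investigators using RECIST 1.1". The Escalation and Expansion objective likewise allows either or both readers. The synopsis (Secondary Endpoints) allows BICR or investigator for DOR, TTP and PFS. Section 1.3.1 makes DOR part of the Expansion Phase primary objective, "To estimate the ORR and duration of response of nivolumab monotherapy in subjects with advanced HCC", where ORR is BICR-read. Section 1.1.6 assigns the 1L cohort's response-related endpoints to independent review.

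**The concern.** Kaplan-Meier assumes that a subject censored at a given time has the same prospects as those still at risk. A subject whose site has just called radiographic progression, but whose scan BICR has not, is unlikely to meet that assumption. Both readers see the same images, so BICR progression is probably near. If scanning ends there and the subject is censored at the last scan, the event is lost and its weight passes to subjects who are doing better.

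Durability of response is part of the clinical-benefit hypothesis for the Expansion Phase (Section 1.2). An inflated BICR DOR would therefore bear on a main conclusion of that phase. TTP and PFS are exposed in the same way wherever BICR is the reader.

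**Working it through.** The plan states no figure on this point, so there is none to reproduce. The check has three steps.

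**1. Who loses scans.**
- Stopped for a reason other than radiographic progression: scans continue to progression.
- Treated beyond progression: scans continue to end of treatment.
- Stopped for radiographic progression: scans end. The 1L wording does not change this, because progression and end of treatment have then both occurred.
- The effort that Section 3.1.8 asks for to document progression after discontinuation concerns symptomatic deterioration without objective progression. It does not cover this group.

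**2. Size under simple disagreement.** Inputs from the documents: median DOR about 12 months (Section 1.1.9) and median TTP 4.2 months (Section 1.4.6). Assumptions: exponential times; a share *d* of investigator progressions is not called by BICR at that scan but would be called 6 weeks later; a share *t* is treated beyond progression and stays on scans; the rest are censored at the last scan. Censoring a fraction *d*(1 − *t*) of events at the event time multiplies the estimated hazard by 1 − *d*(1 − *t*), so approximately

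estimated median = true median / [1 − *d*(1 − *t*)].

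For *d* = 0.2 and *t* = 0: 12 / 0.8 = 15.0 months. For *d* = 0.2 and *t* = 0.5: 12 / 0.9 = 13.33 months. Simulation with 200,000 subjects per scenario gives, for DOR in months:

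| *d* | *t* | Scans continue | Scans stop | Formula | Inflation |
|---|---|---|---|---|---|
| 10% | 0 | 12.13 | 13.32 | 13.33 | +10% |
| 20% | 0 | 12.25 | 14.97 | 15.00 | +22% |
| 30% | 0 | 12.39 | 17.10 | 17.14 | +38% |
| 40% | 0 | 12.58 | 20.07 | 20.00 | +60% |
| 10% | 50% | 12.19 | 12.75 | 12.63 | +5% |
| 20% | 50% | 12.34 | 13.55 | 13.33 | +10% |
| 30% | 50% | 12.41 | 14.31 | 14.12 | +15% |
| 40% | 50% | 12.54 | 15.28 | 15.00 | +22% |

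The comparator slightly exceeds 12 months because the late-called events fall 6 weeks later. For TTP in continuous time, inflation runs from +7% to +47% with *t* = 0 and from +3% to +16% with *t* = 50%.

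**3. Dependence and the scan grid.** A second simulation gave the two readers' progression times equal exponential distributions with correlation *rho* (Gaussian copula), with progression detected only at scheduled scans.
- At *rho* = 0 there is no bias. It needs dependence between the readers.
- For DOR with *rho* of 0.5 or more and *t* = 0, the median on the 6-then-12-week grid moves from 13.8 months (Week 60) to 16.6–19.3 months (Weeks 72–84).
- For TTP the grid median stays at 5.5 months (Week 24) in every scenario. The 26-week estimate rises from 0.40 to 0.43–0.48 for *rho* of 0.5 or more.
- The reason is the grid: 4.2 × 30.4375 / 7 = 18.26 weeks, just past the Week 18 scan. The expected estimates are 0.5^(18/18.26) = 0.505 at Week 18 and 0.5^(24/18.26) = 0.402 at Week 24. The median therefore moves only if the Week 24 estimate rises above 0.5.

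**The case against.** **Unseen rules.** Whether these subjects are censored at the last scan depends on the endpoint definitions in Section 8.3.2. Tables 5.1-8 and 5.1-9 set the follow-up scans, and Sections 5.4 and 5.9 may cover central reads. None of these was in the text reviewed. This stands, and it makes the point conditional: the remedy may already be in Section 8.

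**BICR is optional.** The plan allows either reader for DOR, TTP and PFS. An investigator-read analysis already counts these progressions. In the synopsis the Expansion Phase primary endpoint is ORR alone, with DOR among the secondary endpoints. This stands too, but it does not help any BICR analysis that is reported.

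**Scanning does not stop for everyone.** A reader might infer that all subjects lose scans at investigator progression. The documents do not say that: those treated beyond progression stay on scans until treatment ends, in both 1L arms as well.

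**Later deaths.** A reader might infer that affected subjects can never have an event. Survival follow-up continues (Section 3.7), so PFS is less exposed if later deaths count.

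**Weak inputs.** The 12-month DOR comes from 8 dose-escalation responders (Section 1.1.9) whose responses were investigator-assessed (Section 1.4.6). Every disagreement rate above is assumed. The figures show scale only.

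**Bias between 1L arms.** A reader might infer that nivolumab and sorafenib are biased by different amounts. That would need the share treated beyond progression in each arm, which the documents do not give. The 1L efficacy analysis is also now estimation of ORR, not a comparison.

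**Conclusion.** The concern holds as a conditional one. BICR-read DOR, TTP and PFS are open to informative censoring, and the likely direction is upward. This assumes that affected subjects are censored at their last scan and that the two readers' progression times are positively correlated. The second assumption is reasonable, since both read the same images.

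For DOR the possible inflation is large enough to matter: the 10% to 60% range roughly halves or better once half the subjects stay on scans. The flat statement that all the medians are biased upward is not supported, because the TTP median on the grid did not move under any setting tried. Both the disagreement rate and the share treated beyond progression are unknown here.

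**What to change.** Check Section 8 first. Unless it already does so, prespecify for each BICR-based DOR, TTP and PFS analysis a sensitivity analysis as follows. Where an investigator-assessed radiographic progression ended scanning and BICR has called none, count an event at that scan instead of censoring. Report it beside the BICR estimate, with the number of such subjects per arm, and weigh both when concluding on durability.

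The cost is a paragraph of statistical wording and one further run on data already collected, with no extra scans or reads. The drawbacks are that it mixes readers, can err low where the site over-called progression, and will give a less favourable estimate. It should therefore be presented as a bound and not as the main result.

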#### **Survival Follow Up Phase:**

Survival Follow-Up Visits to occur approximately every 3 months from Follow-Up Visit 2. Survival Follow-up visits may be performed by phone contact or office visit (please refer to [Section 3.7](#)).

### **3.1.2 Duration of Study**

The study is expected to accrue over a period of approximately 4 years. The study will end when survival follow-up collection has concluded. The last visit will be defined as the latest survival visit included in the final analysis of OS (ie. the latest subject death, loss to follow up, or withdrawal of consent). Additional survival follow-up may continue for up to 5 years from the time of this analysis. The study will end once survival follow-up collection has concluded.

### **3.1.3 Dose Escalation Phase**

A 3+3 design with escalating doses will be used with this Phase 1/2 study starting at a dose of 0.3 mg/kg in the non-viral HCC and HCC-HCV arms. Escalations to 1 mg/kg, 3 mg/kg, and 10 mg/kg were originally planned for all cohorts, if safety is demonstrated. Accrual to the HCC-HBV infected arm will begin at 0.1 mg/kg. Subjects will be assigned to a dose level in the order of study entry. For additional risk mitigation, a sentinel dosing strategy will be utilized in the first HBV cohort of 0.1 mg/kg; therefore, two weeks will separate the first nivolumab dose for each subject in the 0.1 mg/kg cohort. However, in subsequent dose panels, a sentinel dosing strategy will not be utilized.

In Amendment 4, given the safety data for the uninfected HCC cohort at the 10 mg/kg dose level and a similar safety profile observed across each HCC etiology, 3 mg/kg dose was selected for Expansion Phase for the uninfected and HCV-infected HCC subjects, whereas a dose of 3 mg/kg or the MTD was planned for the HBV-infected HCC subjects. The HCV- and HBV-HCC cohorts in the dose escalation phase will no longer be escalated to the 10 mg/kg dose. More recently, the HBV 3 mg/kg dose escalation completed at the end of June 2015 with no DLT in any subject; therefore, the HBV expansion arm has opened in July 2015 at the 3 mg/kg dose.

#### **3.1.3.1 Dose Limiting Toxicity in the Dose Escalation Phase**

Dose limiting toxicity (DLT) will be determined based on the incidence and intensity of adverse events (AEs) occurring up to two weeks after the administration of the third dose of nivolumab (ie from C1D1-C1D42).

#### **Dose Limiting Hematologic Toxicity**

DLT will be defined as the need for platelet transfusion, platelet count < 10,000/ $\mu$ L, Grade 4 neutropenia of greater than 3 days duration or febrile neutropenia. The development of a transfusion requirement or an increase in transfusion requirement of more than two units of red blood cells every two weeks over a six week period will also be considered dose limiting unless an alternative cause is identified.

### **3.1.4      *Safety Evaluation of Stage 1 of the Nivolumab plus Ipilimumab Combination Cohort***

A total of 36 subjects will be randomized 1:1:1 (n=12) into one of the following 3 dose arms in Stage 1:

- Arm A--nivolumab 1 mg/kg + ipilimumab 3 mg/kg q3week x 4 (Week 1, 4, 7, and 10) followed by nivolumab 240 mg q2week (beginning at Week 13)
- Arm B--nivolumab 3 mg/kg + ipilimumab 1 mg/kg q3 week x 4 (Week 1, 4, 7, and 10) followed by nivolumab 240 mg q2week (beginning at Week 13)
- Arm C--nivolumab 3 mg/kg q2 week (Week 1, 3, 5, 7, 9, 11, 13, etc) + ipilimumab 1 mg/kg q6week (Week 1, 7, 13, etc).

After enrollment of 36 subjects in Stage 1, no additional subjects will be enrolled until completion of the safety evaluation. Safety and tolerability will be determined when subjects reach week 13, or have been discontinued prior to this time point. However, tolerability beyond four doses may also be taken into consideration. All subjects will continue to be followed for safety, progression, and overall survival after discontinuation of study medication. The criteria used to advance to Stage 2 will be based on drug related adverse events leading to permanent discontinuation in the safety lead-in cohort (Stage 1, n = 12 per dose arm) (listed in [Section 4.1.18](#) for nivolumab and [4.2](#) for ipilimumab) and include the following:

- If no more than one-third of the subjects in a given treatment arm permanently discontinue study medication prior to Week 13 due to treatment related adverse events, then this dose cohort will be deemed as tolerable and enrollment of an additional 28 subjects may proceed (Stage 2).
- If more than one-third of subjects in a treatment arm permanently discontinue study medication prior to Week 13 due to treatment-related adverse events, then the safety, tolerability, and efficacy of that treatment arm will be reviewed by the Sponsor and investigators prior to randomizing any additional subjects. A decision will be made by the sponsor whether to continue enrollment of an additional 28 subjects (Stage 2).

### ***3.1.5      Evaluation of Risk/Benefit for a Cohort that does not meet Tolerability Criteria in the Nivolumab plus Ipilimumab Combination***

In the event that more than 4 of 12 subjects (one-third) per dose arm in Stage 1 require permanent discontinuation due to treatment related adverse events prior to completion of the safety lead-in, the sponsor will review the risk/benefit profile from each cohort and determine whether or not to advance. In this event, the Sponsor will review all available data from Arms A, B, and C, and recommend continuation, modification or termination of a cohort. The rationale for further evaluation is that the most frequent severe drug-related AEs for the combination of nivolumab and ipilimumab have been asymptomatic and reversible (ie, LFTs and lipase laboratory changes) and there is preliminary evidence of deep and durable responses in advanced melanoma (CA209004, CA209067, and CA209069) despite these events. In particular, any assessment of the risk/benefit of a cohort not meeting tolerability will be triggered if the following criteria are met:

- A majority of subjects in the cohort have at least stable disease or a partial tumor response.
- All treatment related AEs leading to discontinuation are non-fatal, reversible and without severe sequela.
- A majority of the treatment related AEs are laboratory in nature, asymptomatic, and monitorable via routine blood draws.

If a decision is made to continue with a cohort because of a favorable risk/benefit profile (ie. non fatal AEs in subjects with at least stable disease or a partial tumor response) and despite meeting the ‘not tolerable’ criteria above, then the EC/IRBs must be notified.

Informed Consent forms updated, and discussion of the risk/benefit must be documented with all current and future subjects who are randomized to this regimen.

